Myelofibrosis	289.83	D75.81
Coagulopathy (other and unspec)	286.9	D68.8, D68.9
Hemophilia	286.52	D68.311
Von Willebrand Disease	286.4	D68.0
Chronic Kidney Disease (not for Renal disease)	585.1	N18.1
	585.2	N18.2
	585.3	N18.3
	585.4	N18.4
	585.5	N18.5
	585.9	N18.9

Table 3. Medications of Interest (Include antiplatelets from [Table 8](#))

Description	GPI codes starting with:	GPI 10

Beta blockers	33	3310004510, 3310004512
Calcium channel blockers	34	3400000710, 3400000310, 3400001010, 3400001011, 3400001012, 3400001015, 3400001050, 3400001300, 3400001500, 3400001810, 3400001812, 3400001814, 3400002000, 3400002200, 3400002400, 3400003010
Antihypertensives	36	3610000510, 3610001000, 3610002010, 3610002510, 3610002710, 3610003000, 3610003310, 3610003510, 3610004010, 3610005000, 3610006000, 3615001020, 3615002010, 3615002420, 3615003000, 3615004020, 3615005520, 3615007000, 3615008000, 3617001010, 3620101010, 3620102510, 3620103000, 3620103010, 3620200510, 3620203010, 3620204010, 3620304000, 3625003000, 3630001010, 3630002010, 3630002500, 3640001010, 3640002000, 3640004010, 3640203010, 3660002010, 3699150220, 3699150223, 3699150270, 3699180215, 3699180225, 3699180235, 3699180240, 3699180255, 3699180260, 3699180265, 3699200210, 3699200213, 3699200220, 3699200230, 3699200240, 3699270250, 3699300205, 3699300210, 3699300270, 3699400210, 3699400220, 3699400225, 3699400230, 3699400245, 3699400250, 3699400260, 3699400270, 3699450320, 3699450345, 3699500220, 3699500270, 3699600215, 3699670210, 3699680320, 3699850250, 3699880260
Diuretics	37	3710001000, 3710001010, 3710002000, 3710003000, 3720001000, 3720002000, 3720002010, 3720003000, 3720008000, 3740001000, 3740003000, 3750001010, 3750002000, 3750002010, 3750003000, 3760001000, 3760002000, 3760002010, 3760002500, 3760004000, 3760005000, 3760005500, 3760006000, 3790003000, 3799000210, 3799000220, 3799000230, 3799200410
Antihyperlipidemics	39	3910001000, 3910001010, 3910001610, 3910002010, 3920000600, 3920002400, 3920002500, 3920002510, 3920003000, 3930003000, 3935001000, 3935002000, 3940001010, 3940003010, 3940005000, 3940005810, 3940006010, 3940006510, 3940007500, 3940990225, 3940990245, 3940990270, 3945005000, 3948005020, 3950003510, 3950004010, 3950004520, 3950005500, 3999400220, 3999400230, 3999900250

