Corticosteroids	22	2210001000, 2210001020, 2210001200, 2210001510, 2210002000, 2210002010, 2210002020, 2210002500, 2210002540, 2210003000, 2210003010, 2210003020, 2210004000, 2210004010, 2210004020, 2210004500, 2210005010, 2210005020, 2210005022, 2210005030, 2210990210, 2210990215, 2210990258, 2210990260, 2210990262, 2210990263, 2210990265, 2210990285, 2210990287, 2210990290, 2210990308, 2210990310, 2210990315, 2210990320, 2210990350, 2210990360, 2210990370, 2210990373, 2210990420, 2220003010

Antidiabetics	27	2710400200, 2710400300, 2710400400, 2710400500, 2710400600, 2710400700, 2710401000, 2710402000, 2710407000, 2710408000, 2710409000, 2715005010, 2717001000, 2717001500, 2717002000, 2717005000, 2720002000, 2720002700, 2720003000, 2720004000, 2720004010, 2720005000, 2720006000, 2725005000, 2728004000, 2728006000, 2730001010, 2730001015, 2730002000, 2730003000, 2730405000, 2730990240, 2750001000, 2750005000, 2755001010, 2755005000, 2755006510, 2755007010, 2757402010, 2760705010, 2760706010, 2770002000, 2770004020, 2770005000, 2799250210, 2799250240, 2799250260, 2799250270, 2799300270, 2799400210, 2799500270, 2799600220, 2799600230, 2799600240, 2799650230, 2799700235, 2799700240, 2799780240, 2799780260, 2799800240, 2799800260, 2799900250
Antiarrhythmics:		
Amiodarone HCl	3540000	3540000500
Propafenone and Flecainide	353000	3530005000
Dronedarone	35400028	3540002810
Betapace (Sotalol)	33100045	33100045
Tikosyn	35400025	3540002500
Disopyramide (Norpace)	35100010	3510001010
Quinidine	351000301	3510003010, 3510003030
Ketoconazole	11404040	1140404000

Table 4. Charlson Comorbidity Index Calculation

Programming algorithm for the Charlson Comorbidity Index (CCI)

1. Identify all patients who ever had the following conditions during their baseline period.

Condition		
Myocardial Infarction	410.x, 412.x	I21.xx, I22.x, I25.2
Congestive Heart Failure	428.x	I50.xx
Peripheral Vascular	441.x, 443.9x,	I71.xx, I73.9, I96, Z95.828

Disease	785.4x, V43.4x	
Cerebrovascular Disease	430.x-438.x	G45.0-G45.2, G45.4-G46.8, I60.xx-I69.xxx (exclude I67.3, I67.83)
Dementia	290.x	F01.5x, F03.90
Rheumatologic Disease	710.0x, 710.1x, 710.4x, 714.0x, 714.1x, 714.2x, 725.x, 714.81	M05.xx-M06.9 (exclude M06.4), M32.xx, M33.20, M34.xx, M35.3
Peptic Ulcer Disease	531.4x-531.7x, 532.4x-532.7x, 533.4x-533.7x, 534.4x-534.7x, 531.0x-531.3x, 532.0x-532.3x, 533.0x-533.3x, 534.0x-534.3x, 531.9x, 532.9x, 534.9x	K25.0-K28.9

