Hypertension	401.x-405.x, 437.2	I10-I16.x, I67.4
Diabetes Mellitus	250.x	E10.xxxx, E11.xxxx, E13.xxxx
Stroke/TIA	433.x1, 434.x1, 435.x, 436, 437.1x, 437.9x, 438.x	G45.0-G45.2, G45.8-G46.2, I63.xxx, I67.8xx, I67.9, I69.xxx
Vascular disease (prior myocardial infarction, peripheral artery disease, or aortic plaque)	410.xx, 412.xx; 440.2x, 443.8x, 443.9x; ICD-9 proc code: 88.48; CPT code: 75710, 75716, 93922, 93923	I21.xx, I22.xx, I25.2, I70.2xx, I73.8x, I73.9, I79.1, I79.8; ICD-10 proc code: B40F0ZZ, B40F1ZZ, B40FYZZ, B40G0ZZ, B40G1ZZ, B40GYZZ, B40J0ZZ, B40J1ZZ, B40JYZZ, B41F0ZZ, B41F1ZZ, B41FYZZ, B41G0ZZ, B41G1ZZ, B41GYZZ, B41J0ZZ, B41J1ZZ, B41JYZZ

After assessing the risk factors and adding up the risk score, the stroke risk classifications are as below:

Score	CHA ₂ DS ₂ -VASc Stroke Risk Classification
0	Low
1	Intermediate
2 or greater	High

Table 7. HAS-BLED Bleed Risk Score

HAS-BLED Criteria		
Hypertension	401.x-405.x	I10-I16.x
	Drugs used to treat hypertension (GPI codes 3300, 3400, 3610, 3615, 3620, 3625, 3630, 3640, 3660, 3720, 3760)	
Abnormal renal and liver function	Renal: 580.xx-586.xx, V56.0, V56.8; ICD-9 procedure codes 39.95, 54.98; CPT codes 90935-90993, 99512, 99559	N00.0-N08, N17.0-N19, Z49.31, Z49.32; ICD-10 procedure code: 3E1M39Z, 5A1D00Z, 5A1D60Z

(1 point for each)	Liver: 070.x, 155.0x, 155.1x, 155.2x, 571.x, 572.x, 573.x, 576.8, 456.0x, 456.1x, 456.2x; ICD-9 procedure codes 39.1x, 42.91	B15.x-B19.xx, C22.x, I85.xx, K70.xx, K71.xx, K72.01-K76.1, K76.3-K77, K83.5; ICD10 procedure code: 0610xxx, 0611xxx, 0612xxx, 0614xxx, 0615xxx, 0616xxx, 0617xxx, 0618xxx, 0619xxx, 061Bxxx, 061Jxxx, 06L30CZ, 06L30DZ, 06L30ZZ, 06L33CZ, 06L33DZ, 06L33ZZ, 06L34CZ, 06L34DZ, 06L34ZZ
Stroke	433.xx-437.xx	G45.x, G46.x, I63.xxx-I66.9, I67.1, I67.2, I67.4-I67.82, I67.84x-I68.8

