Bleeding (includes anemia and other prior hemorrhage)	285.0x, 285.1x, 285.9x, 423.0x, 430.x-432.x, 455.2x, 455.5x, 455.8x, 459.0x, 531.0x, 531.2x, 531.4x, 531.6x, 532.0x, 532.2x, 532.4x, 532.6x, 533.0x, 533.2x, 533.4x, 533.6x, 534.0x, 534.2x, 534.4x, 534.6x, 562.02, 562.03, 562.12, 562.13, 568.81, 569.3, 569.83, 569.85, 569.86, 578.0, 578.1, 578.9, 599.7x, 719.1x, 784.7x, 786.3x; ICD-9 procedure code 44.43; CPT code 43255	D62, D64.0, D64.1, D64.2, D64.3, D64.9, I31.2, I60.xx, I61.x, I62.xx, K25.0, K25.2, K25.4, K25.6, K26.0, K26.2, K26.4, K26.6, K27.0, K27.2, K27.4, K27.6, K28.0, K28.2, K28.4, K28.6, K55.21, K57.11, K57.13, K57.31, K57.33, K62.5, K63.1, K63.81, K64.4, K64.8, K66.1, K92.0, K92.1, K92.2, M25.0xx, R04.0, R04.2, R04.81, R04.89, R04.9, R31.0, R31.1, R31.21, R31.29, R31.9, R58; ICD-10 procedure code: 0W3P8ZZ
Labile INRs		
Elderly (Age >65 years)	-	
Drug or alcohol abuse (1 point for each)	Drug: NSAIDs (GPI codes 6410, 6610), Anti-platelets (8515), Other aspirin-containing products (3940990215, 4399100222, 4399100223, 4399100232, 4399100405, 4399400321, 4399400456, 4399590415, 4399590419, 6030990225, 6499000220, 6499000221, 6499000225, 6499000226, 6499000232, 6499000320, 6499000321, 6499000335, 6499000340, 6499000450, 6499000460, 6499100220, 6499100222, 6499100228, 6499100330, 6499100335, 6599000222, 6599100210, 6599100220, 6599100325, 6599100430, 6599100510, 6599170220, 6599400220, 7599000210, 7599000240, 7599000310, 7599000320, 8515990220, 9990000000)	

	Alcohol: 291.xx, 303.xx, 305.0x, 357.5x, 425.5x, 571.1x, 571.2x, 571.3x; ICD-9 procedure codes 94.61-94.63, 94.67-94.69	F10.xxx, G62.1, I42.6, K70.xx; ICD-10 procedure code: HZ2ZZZZ, HZ30ZZZ, HZ31ZZZ, HZ32ZZZ, HZ33ZZZ, HZ34ZZZ, HZ35ZZZ, HZ36ZZZ, HZ37ZZZ, HZ38ZZZ, HZ39ZZZ, HZ3BZZZ, HZ40ZZZ, HZ41ZZZ, HZ42ZZZ, HZ43ZZZ, HZ44ZZZ, HZ45ZZZ, HZ46ZZZ, HZ47ZZZ, HZ48ZZZ, HZ49ZZZ, HZ4BZZZ, HZ50ZZZ, HZ51ZZZ, HZ52ZZZ, HZ53ZZZ, HZ54ZZZ, HZ55ZZZ, HZ56ZZZ, HZ57ZZZ, HZ58ZZZ, HZ59ZZZ, HZ5BZZZ, HZ5CZZZ, HZ5DZZZ, HZ63ZZZ, HZ83ZZZ, HZ86ZZZ, HZ88ZZZ, HZ89ZZZ, HZ93ZZZ, HZ96ZZZ, HZ98ZZZ, HZ99ZZZ
--	---	---

*the maximum score will be 8 since we do not have data available for labile INRs

After assessing the risk factors and adding up the score, the bleed risk classifications are as follows:

Score	HAS-BLED Bleed Risk Classification
0-1	Low
2	Intermediate
3 or greater	High

Table 8. Atrial Fibrillation Medications

Rate control medications	GPI codes starting with:	GPI 10
Beta blockers	3300	3310004510, 3310004512

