Calcium channel blockers		3400000710, 3400000310, 3400001010, 3400001011, 3400001012, 3400001015, 3400001050, 3400001300, 3400001500, 3400001810, 3400001812, 3400001814, 3400002000, 3400002200, 3400002400, 3400003010
Verapamil	34000030100	3400003010
Diltiazem	340000101	3400001010, 3400001011, 3400001012, 3400001015, 3400001050
Digoxin/digitoxin	321000	3120001000
Dronedarone	35400028100320	3540002810
Amiodarone	3540000500	3540000500
Rhythm control medications		
Disopyramide (Norpace)	35100010	3510001010
Procainamide	3510002010	3510002010

Flecainide	3530001	3530001010
Propafenone	3530005	3530005000
Betapace (Sotalol)	33100045	3310004510, 3310004512
Tikosyn (Dofetilide)	35400025	3540002500
Quinidine	351000301	3510003010, 3510003030
Mexiletine	352000251	not exist
Moricizine	35050301003	not exist
Other		
ACE Inhibitors	3610	36100005, 36100010, 36100020, 36100025, 36100027, 36100030, 36100033, 36100035, 36100040, 36100050, 36100060
Angiotensin-II Receptor Blockers (ARB)	3615	3615004020, 3615003000, 3615002010, 3615008000, 3615005520, 3615007000, 3615002420, 3615001020
Diuretics (Thiazide, loop)	3720, 3760	3710001000, 3710001010, 3710002000, 3710003000, 3720001000, 3720002000, 3720002010, 3720003000, 3720008000, 3740001000, 3740003000, 3750001010, 3750002000, 3750003000, 3760001000, 3760002000, 3760002010, 3760002500, 3760004000, 3760005000, 3760005500, 3760006000, 3790003000, 3799000210, 3799000220, 3799000230, 3799200410
Antihypertensives (excluding above group)	3620, 3625, 3630, 3640, 3660	3610000510, 3610001000, 3610002010, 3610002510, 3610002710, 3610003000, 3610003310, 3610003510, 3610004010, 3610005000, 3610006000, 3615001020, 3615002010, 3615002420, 3615003000, 3615004020, 3615005520, 3615007000, 3615008000, 3617001010, 3620101010, 3620102510, 3620103000, 3620103010, 3620200510, 3620203010, 3620204010, 3620304000, 3625003000, 3630001010, 3630002010, 3630002500, 3640001010, 3640002000, 3640004010, 3640203010, 3660002010, 3699150220, 3699150223, 3699150270, 3699180215, 3699180225, 3699180235, 3699180240, 3699180255, 3699180260, 3699180265, 3699200210, 3699200213, 3699200220, 3699200230, 3699200240, 3699270250, 3699300205, 3699300210, 3699300270, 3699400210, 3699400220, 3699400225, 3699400230, 3699400245, 3699400250, 3699400260, 3699400270, 3699450320, 3699450345, 3699500220, 3699500270, 3699600215, 3699670210, 3699680320, 3699850250, 3699880260

Fondaparinux	83103030	8310303010 (Also include HCPCS code: Injection, fondaparinux sodium, 0.5 mg - J1652)

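### Appendix A gives three inconsistent code definitions for beta blockers (prefix 33, prefix 3300, and a ten-digit list identical to the sotalol list), and no rule says which one governs.

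*Combined protocol and SAP*

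**What the plan says.** Section 9.3.3 (Covariates) defines use of other medications as any fill in the pre-index period and refers to Appendix A, Tables 3 and 8 for the codes. Both tables have a prefix column, headed "GPI codes starting with", and beside it a column of ten-digit GPI codes. In the two beta-blocker rows and in Table 8's sotalol row, the ten-digit entry is the same: "3310004510, 3310004512".

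- Table 3: "Beta blockers 33 3310004510, 3310004512"
- Table 8, under rate control: "Beta blockers 3300 3310004510, 3310004512"
- Table 8, under rhythm control: "Betapace (Sotalol) 33100045 3310004510, 3310004512"
- Table 7 (HAS-BLED), hypertension row: "Drugs used to treat hypertension (GPI codes 3300, 3400, 3610, 3615, 3620, 3625, 3630, 3640, 3660, 3720, 3760", listed with the diagnosis codes "401.x-405.x I10-I16.x"

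Section 9.7 (Data Analysis) names baseline medication use and the modified HAS-BLED score among the characteristics to be considered for the propensity score. It leaves the final list to be agreed with the sponsor. Nothing in the protocol says whether the prefix column or the ten-digit column is operative.

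**The concern.** A programmer building the beta-blocker flag finds two tables cited for one covariate, two prefixes, and a ten-digit list that belongs to another row. Each choice yields a different variable, and the plan does not choose.

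Propensity score matching is the main control for confounding in both comparisons. If the flag is built from the ten-digit list, the model and the balance table would describe sotalol use under a beta-blocker label, and apparent balance on that line would say nothing about the rest of the class. HAS-BLED, another candidate for the score, takes its hypertension drugs from the 3300 prefix and so inherits part of the problem.

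**Working it through.** The plan states no figure on this point. The check compares the code strings that the tables themselves give.

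**Inputs.** Listed beta-blocker codes (Tables 3 and 8): 3310004510 and 3310004512. Prefixes: 33 (Table 3), 3300 (Table 8), 33100045 (sotalol, Tables 3 and 8), and the eleven HAS-BLED drug prefixes (Table 7).

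**Test.** Does each listed code begin with the prefix?

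| Rule | Listed codes contained |
|---|---|
| 33 (Table 3, beta blockers) | 2 of 2 |
| 3300 (Table 8, beta blockers) | 0 of 2 |
| 33100045 (sotalol) | 2 of 2 |
| All eleven HAS-BLED prefixes (Table 7) | 0 of 2 |

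Both codes begin 3310, so neither can begin 3300. The beta-blocker and sotalol lists in Table 8 are identical.

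**What each reading of the covariate yields.**
1. Prefix 33: every code beginning with 33, sotalol included.
2. Ten-digit list: sotalol only.
3. Prefix 3300: codes beginning 3300, sotalol excluded.

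Readings 2 and 3 have no code in common, yet they stand in the same row of Table 8.

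**HAS-BLED.** Table 7 gives a maximum of 8 without labile INR: hypertension 1, renal 1, liver 1, stroke 1, bleeding 1, age 1, drugs 1, alcohol 1, which sums to 8. Hypertension is therefore worth one point. The row lists diagnosis codes as well as eleven drug prefixes, of which 3300 is the only one beginning with 33. Read so that either a diagnosis or a drug qualifies, the score changes only for a patient who has no listed hypertension diagnosis, no drug under the other ten prefixes, and a drug coded 33 but not 3300. That patient's score is one point too low, which can move the risk class by one step (0–1, 2, 3 or more).

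**Other rows where the two columns disagree.**
- Digoxin, Table 8: prefix 321000, ten-digit code 3120001000; 0 of 1 contained.
- Diuretics, Table 8: prefixes 3720 and 3760; 13 of the 27 listed codes contained. The other 27 − 13 = 14 begin 3710, 3740, 3750, 3790 or 3799.
- "Propafenone and Flecainide", Table 3: prefix 353000, ten-digit code 3530005000 only. Table 8 gives flecainide as 3530001010, which the prefix contains and the ten-digit cell omits.

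**The case against.** The strongest reply is that the tables already contain a workable rule. The prefix column reads as a selection rule, Table 3's prefix 33 covers every code beginning with 33, and a sensible programmer would use it. This stands in part. A reader might infer that beta blockers are coded as sotalol and nothing else, or that the covariate is bound to be mismeasured. The documents do not support that: it is true of the ten-digit column only, and it does not follow under prefix 33. But Section 9.3.3 cites Table 8 as well, where the prefix is 3300, and nothing ranks one table or column above the other.

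Other stronger readings also fail.

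- **Most beta-blocker users would be missed.** This needs the prevalence of beta-blocker and sotalol use, which the documents do not give, and it would apply to one reading of three. Which other drugs 3300 covers cannot be settled from the documents either.
- **Sotalol users are wrongly counted twice.** The flags are separate ever-filled indicators, and nothing makes the classes exclusive. Verapamil and diltiazem codes, for instance, repeat codes in the calcium-channel-blocker row. Whether sotalol belongs in one class or both is a choice to be stated.
- **Flecainide is lost.** Only under the ten-digit column; prefix 353000 captures it.
- **HAS-BLED is badly distorted.** Hypertension has many other triggers in Table 7.
- **Beta-blocker use is a leading covariate.** It is one of eleven drug classes, and the final propensity list is undecided.

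Nor is it enough to declare the prefix column operative throughout. In Table 8 that would miss the listed digoxin code and drop 14 listed diuretic codes.

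**Conclusion.** The contradiction is real and visible without any outside drug reference. Tables 3, 7 and 8 hold three incompatible beta-blocker definitions. Table 8's row contradicts itself, and Table 7's only 33-series prefix cannot capture the codes that the plan lists as beta blockers.

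The consequence depends on what is programmed: sotalol only under the ten-digit list, both listed codes missed under 3300, and neither fault under 33. The HAS-BLED effect is at most one point, in the narrow group described above, assuming that a diagnosis or a drug alone is sufficient. Neither the number of misclassified patients nor the effect on the treatment comparisons can be derived from the documents. This should be corrected because the code lists are operative and the correction is cheap; no bias in the results has been shown.

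**What to change.** 1. Use one beta-blocker definition in Tables 3, 7 and 8. Table 3's prefix 33 is the only stated rule that contains the listed codes and is not limited to sotalol. Replace 3300 in Tables 7 and 8 accordingly.
2. Correct the ten-digit beta-blocker cells in Tables 3 and 8 so that they list the intended class.
3. State whether sotalol counts as a beta blocker, an antiarrhythmic, or both.
4. State, row by row, which column governs. Reconcile the digoxin row (321000 against 3120001000), the Table 8 diuretic row (3720 and 3760 against the 3710, 3740, 3750, 3790 and 3799 codes), and the Table 3 propafenone/flecainide cell (add 3530001010, or state that prefix 353000 governs).

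The cost is an edit to the code lists; no new data are needed. Section 6 (Milestones) dates the development of programming rules from 19 October 2016 and data analysis from 05 December 2016, so first check which column was used. If the flag was built from the ten-digit list or from 3300, rebuild it, recompute HAS-BLED where 3300 was used, and repeat the propensity model and matching if either variable entered it.

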
>30 days
 
Patients need at least two days of exposure to the index NOAC to ensure they had at least one day of index NOAC exposure in the post-index follow-up period. A sensitivity analysis will also be performed using a 14 day treatment gap.
 
Both claims-level data, including diagnosis codes, procedure codes, pharmacy dispensed drugs, cost information, and enrolment data, as well as EHR-level data, including relevant lab tests and results, will be extracted for all applicable patients. Patient demographics, treatment history, and comorbidities, will be derived from the electronic database. Start and stop dates of each course of treatment will be coded from the pharmacy and medical claims data using rules to be developed in the study protocol. Comorbidities of interest will be ascertained through ICD-9 and ICD-10 diagnosis codes, in combination with procedures and medications, as appropriate to the study protocol definitions.
 
To account for potential selection bias, the study cohorts (dabigatran/rivaroxaban and dabigatran/apixaban) will be matched on their baseline characteristics using the propensity score matching (PSM) method. The PSM aims to balance the two treatment groups on baseline demographics, health plan type and clinical characteristics. The feasibility of PSM will be evaluated based on available sample size and descriptive results. If patient characteristics between dabigatran/rivaroxaban and dabigatran/apixaban cohorts are significantly different, i.e., less than 50% of patients in the dabigatran group can be matched to the rivaroxaban or apixaban group based on PSM, then the study design will be re-evaluated before proceeding to analysis. The Nearest Neighbor method of propensity score matching within a caliper of 0.10-0.20 (depending on resulting sample sizes) of the standard deviation of the estimated logit will be used to select the matched samples.
 
The propensity score models will include baseline variables known to be confounders or factors related to the outcome only, including age, gender, health plan type, geographic region, month and year of index date, Charlson comorbidity index (CCI), stroke risk scores (i.e. CHADS₂ or CHA₂DS₂-VASc), bleeding risk scores (i.e., modified HAS-BLED), specified comorbid conditions and medication use, based on literature and clinical relevance, as well as empirical data (top diagnoses, procedures, etc.) that may account for possible unforeseen confounding.

--

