ANNEX 1. LIST OF STAND-ALONE DOCUMENTS

APPENDIX A. VARIABLE CODING LIST**Table 1. NOACs for Exposure**

Class	Description	GPI Code
Direct thrombin inhibitors	Dabigatran	833370302001
Direct Xa inhibitor	Rivaroxaban Apixaban	83370060 83370010

Table 2. Baseline Comorbid Conditions

Comorbidity		
Cancer	140.xx-172.xx, 174.xx-208.xx, 230.xx-231.xx, 233.xx-234.xx	C00.xxx-D49.xxx
Rheumatoid arthritis	714.xx	M05.xxx, M06.xxx, M08.xxx, M12.0xx
Multiple sclerosis	340	G35
Coronary artery disease	411.xx, 412.xx, 413.xx, 414.xx, 429.2	I20.x, I24.x, I25.xxx
Acute myocardial infarction	410.xx	I21.xx
Cardiomyopathy	425.xx	I42.x, I43
Ischemic stroke	433.x1, 434.x1, 436.x	I63.xxx, I67.89
TIA	435.x	G45.0, G45.1, G45.2, G45.8, G45.9, G46.0, G46.1, G46.2
Heart failure	402.x1, 404.x1, 404.x3, 428.xx	I11.0, I13.0, I13.2, I50.1, I50.2x, I50.3x, I50.4x, I50.9
Atrial flutter	427.32	I48.92
Hypertension	401.x, 402.x0, 403.xx, 404.x0, 404.x2, 405.xx	I10, I11.9, I12.x, I13.1x, I15.x, I16.x
Peripheral artery disease	440.xx, 443.xx	I70.xxx, I73.xx, I77.7x, I79.1, I79.8
Liver disease	121.1, 423.2, 570-573.xx, 751.62	B661, I311. K70.0-K77, Q446
Renal disease	580.xx-588.xx,	N0x.x, N08, B52.0, E08.2x, E09.2x, N14.x, N15.x, N17.x, N18.x, N19, N25.0, N25.1, N25.9, N25.81, N25.89, N26.x,
	590.xx-593.xx	N10, N11.x, N12, N13.0, N13.0, N13.1, N13.2, N13.30, N13.39, N13.4, N13.5, N13.6, N13.70, N13.71, N13.732, N13.729, N13.721, N13.731, N13.722, N13.739, N13.8, N13.9, N15.x, N16, N20.x, N22, N28.1, N28.0, N28.81, N28.83, N28.84, N28.85, N28.86, N28.89, N28.9, N29, R80.2
COPD/emphysema	490-492.xx, 496	J40.x-J44.x

Hypothyroidism	243-244.x	E00.x, E01.8, E02, E03.0, E03.1, E03.2, E03.3, E03.4, E03.8, E03.9, E89.0
Diabetes	250.xx	E10.xxxx, E11.xxxx, E13.xxxx
Peptic ulcer/GERD	530.11, 530.81, 536.2, 536.8, 787.1, 533.xx	K21.x, K27.x, K30, R11.10, R12
Venous thromboembolism	415.11, 415.19, 451.1x, 451.2, 451.81, 451.83, 451.84, 451.9, 453.4x, 453.8x, 453.9	I2699, I80.1x-I80.9, I82.4xx, I82.6xx, I82.890, I82.90, I82.A1x, I82.B1x, I82.C1x
Hyperlipidemia	272.0 – 272.4	E78.0x-E78.5
HIV infection	V08, 042, 079.53	Z21, B20, B97.35
Bone Marrow disease		
Thrombocytopenia	287.3, 287.4, 287.5	D69.3, D69.4x, D69.5x, D69.6
Chronic anemia	285.2	D63.x
Myelofibrosis	289.83	D75.81
Coagulopathy	286.0-286.9, 287.1, 287.3-287.5	D65-D68.x, D69.1, D69.3-D69.6
Dyspepsia	536.8	K30
Left ventricular heart failure	428.1	I50.1
Bone marrow disease	289.9	D75.9
Thrombocytopenia	287.5	D69.6
Anemia	285.9	D64.9

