Anticoagulants		
Dabigatran	833370302001	8333703020
Argatroban	83337015	8333701500, 8333701520
Warfarin	83200030	8320003020
Heparin	83100020	8310002020, 8310002022, 8310002025, 8310002030, (Also include HCPCS code: Injection, heparin sodium, (heparin lock flush), per 10 units - J1642 , Injection, heparin sodium, per 1000 units - J1644)
Enoxaparin	83101020	8310102010 (Also include HCPCS code: Injection, enoxaparin sodium, 10 mg - J1650)
Tinzaparin	83101080	not exist in GPI database (Include HCPCS code: Injection, tinzaparin sodium, 1000 iu - J1655)
Dalteparin	83101010	8310101010 (Also include HCPCS code: Injection, dalteparin sodium, per 2500 iu - J1645)
Rivaroxaban	83370060	8337006000
Apixaban	83370010	8337001000
Antiplatelet		
Clopidogrel	85158020	8515802010
Brilinta (ticagrelor)	85158470	8515847000
Prasugrel	85158060100330, 85158060100320	8515806010
Ticlopidine	85158080100320	8515808010
Cilostazol	85155516000320, 85155516000330	8515551600
Dipyridamole	85150030000310, 85150030000320, 85150030000330	8515003000
NSAIDs	6610	6610007000, 6610003000, 6610002000, 6610004010, 6610001010, 6610006000, 6610008000, 6610006010, 6610009010, 6610001200, 6610005000, 6610006500, 6610003500, 6610000710, 6610101000, 6610000720, 6610000800, 6610003710, 6610990220, 6610052500, 6610005200, 6610005500, 6610003010, 6610002040, 6610006050, 6610002050, 6610990328, 6610990244, 6610005260, 6610990232, 6610000700, 6610990241, 6610990340, 6610990435, 6610990337, 6610990217, 6610990338, 6610990256, 6610990440, 6610990339, 6610990315, 6610990317,

		6610990238,
--	--	-------------

Table 9. Outcome Codes

Medical Conditions	ICD-9 Codes	Description	ICD-10 Codes
Stroke		Inclusive of ischemic stroke and hemorrhagic stroke below	
Major Bleeding		Inclusive of hemorrhagic stroke, major intracranial bleeding and major extracranial bleeding below	
Ischemic Stroke (Primary Only)	433.x1	Occlusion and stenosis of precerebral arteries with cerebral infarction	I63.xxx
	434.x1	Occlusion of cerebral arteries with cerebral infarction	
	436	Acute, but ill-defined, cerebrovascular disease	I67.89
	Exclusion	EXCLUDE above codes if hospitalization lasted <48 hours and was accompanied by carotid endarterectomy (ICD-9 procedure code 38.1)	
Hemorrhagic Stroke (Primary Only)			
	431	Intracerebral hemorrhage (ICH)	I61.x

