	Exclusion	EXCLUDE above codes if “traumatic brain injury” ICD-9-CM code (800 to 804, 850 to 854) or “rehabilitation care” as the primary ICD-9-CM code (V57) is present.	S02.xxxA, S02.xxxB, S06.xxxA, Z51.89
Major Intracranial Bleeding (Primary or Secondary)	430	Subarachnoid hemorrhage	I60.xx
	431	Intracerebral hemorrhage	I61.x
	432.x	Other and unspecified intracranial hemorrhage	I62.xx
	852.0	Subarachnoid hemorrhage following injury without mention of open intracranial wound	S06.36xA
	852.2	Subdural hemorrhage following injury without mention of open intracranial wound	S06.4XXA
	852.4	Extradural hemorrhage following injury without mention of open intracranial wound	S06.5XXA
	853.0	Other and unspecified intracranial hemorrhage following injury without mention of open intracranial wound	S06.6XXA

	Exclusion	EXCLUDE – above codes if concomitant discharge diagnosis of major trauma was present (ICD-9 codes 852.1, 852.3, 852.5, and 853.1)	S01.90XA, S06.36xA, S06.4XxA, S06.5XxA, S06.6XxA
Major Extracranial		Inclusive of major GI bleeding, major urogenital bleeding and major other bleeding	
Major GI Bleeding		Inclusive of major upper GI bleeding and major lower GI bleeding	
Major upper GI bleed (Primary Only)	531.0x	Acute gastric ulcer with hemorrhage with/without obstruction	K25.0
	531.2x	With hemorrhage and perforation with/without obstruction	K25.2
	531.4x	(chronic or unspecified gastric ulcer with hemorrhage with/without obstruction)	K25.4
	531.6x	(with hemorrhage and perforation with/without obstruction)	K25.6
	532.0x	(acute duodenal ulcer with hemorrhage with/without obstruction)	K26.0
	532.2x	(with hemorrhage and perforation with/without obstruction)	K26.2
	532.4x	(chronic or unspecified duodenal ulcer with hemorrhage with/without obstruction)	K26.4
	532.6x	(with hemorrhage and perforation with/without obstruction)	K26.6
	533.0x	(acute peptic ulcer of unspecified site with hemorrhage with/without obstruction)	K27.0
	533.2x	(with hemorrhage and perforation with/without obstruction)	K27.2
	533.4x	(chronic or unspecified peptic ulcer of unspecified site with hemorrhage with/without obstruction)	K27.4
	533.6x	(with hemorrhage and perforation with/without obstruction),	K27.6
	534.0x	(acute gastrojejunal ulcer with hemorrhage with/without obstruction)	K28.0
	534.2x	(with hemorrhage and perforation with/without obstruction)	K28.2
	534.4x	(chronic or unspecified gastrojejunal ulcer with hemorrhage with/without obstruction)	K28.4

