	534.6x	(with hemorrhage and perforation with/without obstruction)	K28.6

	578.0	(hematemesis)	K92.0
	ICD-9 Procedure Code 44.43	(endoscopic control of gastric or duodenal bleeding)	
	CPT code 43255	(upper gastrointestinal endoscopy including esophagus, stomach, and either the duodenum and/or jejunum as appropriate with control of bleeding, any method)	
Major lower GI bleeding (Primary Only)	562.02	Diverticulosis of small intestine with hemorrhage	K55.21
	562.03	Diverticulitis of small intestine with hemorrhage	K57.11
	562.12	Diverticulosis of colon with hemorrhage	K57.13
	562.13	Diverticulitis of colon with hemorrhage	K57.31
	569.3x	Hemorrhage of rectum and anus	K57.32
	569.85	Angiodysplasia of intestine with hemorrhage	K62.5
	578.1x	Blood in stool	K92.1
	578.9	Hemorrhage of GI tract, unspecified	K92.2
Major urogenital bleed (Primary Only)	599.7	Hematuria	R31.0 - R31.29
	626.2x and (280.0, 285.1 or 285.9)	Excessive/frequent menstruation and secondary diagnosis indicating acute bleeding (anemia)	N92.0 and (D50.0, D62, D64.9)
Other major bleeds (Primary Only)	719.1x	Hemathrosis	D62
	423.0x	Hemopericardium	I31.2
	786.3x	Hemoptysis	M25.0xx
	784.7x	Epistaxis	R04.0
	459.0x	Hemorrhage not specified	R04.2
	285.1x	Acute posthemorrhagic anemia	R04.8x, R04.9, R58
TIA (Primary Only)	435.x	Transient cerebral ischemia as the principal (primary) discharge diagnosis	G45.0, G45.1, G45.8, G45.9, G46.0, G46.1, G46.2
[REDACTED]	[REDACTED]	[REDACTED]	[REDACTED]
[REDACTED]		[REDACTED]	
[REDACTED]	[REDACTED]	[REDACTED]	[REDACTED]
[REDACTED]	[REDACTED]	[REDACTED]	[REDACTED]

APPENDIX B: Inclusion and exclusion diagnosis, procedure and CPT codes**Table 1. List of codes for atrial fibrillation**

Study Inclusion DX	ICD9 Diagnosis Codes	ICD10 Diagnosis Codes
Atrial Fibrillation	427.31	I48.0, I48.1, I48.2, I48.91

Table 2. List of codes and descriptions to identify patients with exclusion diagnoses

Study Exclusion DX	ICD9 Diagnosis Codes	ICD10 Diagnosis Codes
Hyperthyroidism	242.x	E05.00, E05.01, E05.10, E05.11, E05.20, E05.21, E05.30, E05.31, E05.40, E05.41, E05.80, E05.81, E05.90, E05.91
Orthopedic Procedures (See also procedure codes)	V43.64, V43.65	Z9664x, Z9665x
DVT	451.xx, 453.xx	I80.xxx, I82.xxx
PE	415.1x	I26.01, I26.09, I26.90, I26.92, I26.99, I27.82
Pericarditis	391.x, 393, 420.x, 423.2, 036.41, 074.21, 093.81, 098.83	A39.53, B33.23, I01.0, I09.2, I30.0, I30.1, I30.8, I30.9, I31.0, I32, M32.12

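### Table 9's carotid endarterectomy exclusion has no ICD-10 procedure code, so the primary stroke outcome is broader in the ICD-10 period; two smaller code gaps run the other way

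*Combined protocol and SAP*

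**What the plan says.** Table 9 (Annex 1, Appendix A) defines the outcomes in separate ICD-9 and ICD-10 columns.

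- **Ischemic stroke, part of the primary stroke outcome.** The diagnoses are 433.x1, 434.x1 and 436 in ICD-9, and I63.xxx and I67.89 in ICD-10, in primary position. Stays under 48 hours are excluded if the admission "was accompanied by carotid endarterectomy (ICD-9 procedure code 38.1"). The ICD-10 cell of that row is empty.
- **Hemorrhagic stroke.** Its exclusion does carry ICD-10 codes: "S02.xxxA, S02.xxxB, S06.xxxA, Z51.89".
- **Major upper GI bleed, part of primary major bleeding.** ICD-9 procedure 44.43 ("endoscopic control of gastric or duodenal bleeding") has an empty ICD-10 cell. The next row lists CPT 43255: "upper gastrointestinal endoscopy including esophagus, stomach, and either the duodenum and/or jejunum as appropriate with control of bleeding, any method".
- **TIA, secondary.** Beside 435.x, the ICD-10 list is "G45.0, G45.1, G45.8, G45.9, G46.0, G46.1, G46.2".

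Elsewhere in Appendix A, the HAS-BLED bleeding row of Table 7, which also carries 44.43, ends with "ICD-10 procedure code: 0W3P8ZZ". The baseline TIA row of Table 2, beside the same 435.x, lists "G45.0, G45.1, G45.2, G45.8, G45.9, G46.0, G46.1, G46.2".

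Both coding systems are in use. The Abstract says of baseline conditions that "Comorbidities of interest will be ascertained through ICD-9 and ICD-10 diagnosis codes", and Table 9 has its own ICD-10 column. Section 9.2 ends both comparisons on 30 June 2016.

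**The concern.** An outcome definition should mean the same thing throughout follow-up. Here a rule that removes events from a primary outcome is tied to a code that exists in only one coding system. Once ICD-10 coding begins, the listed codes leave the rule without a trigger, and some short carotid surgery stays that ICD-9 coding would have removed remain as strokes. The other two gaps can drop events from upper GI bleeding and from TIA.

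At stake are the event rates per person-time that Section 9.7.1 plans for every outcome, and the use of a single outcome definition within each Cox model. The planned rates are stratified by age and gender, not by coding era, so nothing in the plan would reveal the change.

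**Working it through.** **1. Code lists side by side**

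| Item | ICD-9 side | ICD-10 side in Table 9 | Elsewhere in Appendix A | Direction in ICD-10 period |
|---|---|---|---|---|
| Endarterectomy exclusion | procedure 38.1 | none | none | events kept |
| Endoscopic bleeding control | procedure 44.43 | none | 0W3P8ZZ (Table 7) | events can be lost |
| TIA | 435.x | 7 codes | 8 codes (Table 2) | events can be lost |

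For TIA, Table 2 minus Table 9 leaves G45.2 only, and Table 9 minus Table 2 leaves nothing. The range G45.0-G45.2 in Tables 5 and 6 also covers G45.2.

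**2. Omission or choice?** Every other row with ICD-9 procedure codes also lists ICD-10 procedure codes: vascular imaging in Table 6; dialysis, liver procedures, bleeding control and alcohol treatment in Table 7; and valve, hip, knee and cardiac procedures in Appendix B, Table 3. The two ICD-9 procedure entries without a partner, 38.1 and 44.43, are both in the outcome table. No other section supplies the missing outcome codes.

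**3. Calendar time affected.** The documents give no switch date. The windows in Section 9.2 are 60 months (rivaroxaban) and about 42 months (apixaban). If the last *m* months are ICD-10 coded, the share is *f* = *m*/60 or *m*/42. An October 2015 switch gives *m* = 9; values of 6 and 12 show the sensitivity.

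**4. Size for ischemic stroke.** Let *p* be the share of ICD-10-coded discharges meeting the stroke diagnosis codes that are short endarterectomy stays. The documents give no value; 2-10% is assumed. The excess in the ICD-10 period is *p*/(1 − *p*):

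- *p* = 0.02: 0.02/0.98 = 2.0%
- *p* = 0.10: 0.10/0.90 = 11.1%

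If events are spread evenly over the window, the whole-study excess is *f* × *p*/(1 − *p*):

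| *m* | Rivaroxaban: *f* | Excess | Apixaban: *f* | Excess |
|---|---|---|---|---|
| 6 | 10% | 0.2-1.1% | 14% | 0.3-1.6% |
| 9 | 15% | 0.3-1.7% | 21% | 0.4-2.4% |
| 12 | 20% | 0.4-2.2% | 29% | 0.6-3.2% |

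Overall stroke is affected proportionally less, because it also contains hemorrhagic stroke, which this exclusion does not touch.

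**5. Between-arm effect.** With excess *e* = *p*/(1 − *p*) and ICD-10-era shares *f*₁ and *f*₀ in the two arms, the ischemic stroke rate ratio is multiplied by (1 + *e f*₁)/(1 + *e f*₀), roughly 1 + *e*(*f*₁ − *f*₀). If the shares are equal, the factor is 1. At *e* = 11.1%, each percentage point of difference moves the ratio by about 0.111 × 1% = 0.11%.

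**The case against.** The case against has several parts.

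- **The endarterectomy rule is stated in words.** It applies to the listed diagnoses, which include the ICD-10 ones, and the ICD-9 number is in parentheses. A programmer who follows the intent would map it. That stands as a reading of intent, but the plan supplies no mapping, and literal programming gives a different outcome. Nor are all elective carotid stays affected: only those with a primary I63.xxx or I67.89 code.
- **The upper GI gap is partial.** CPT 43255 belongs to neither ICD version, Section 9.4 says encounter data include CPT procedure codes, and the ICD-10 bleeding diagnoses still apply. This stands. Table 7's row also pools many bleeding sites, so 0W3P8ZZ is not shown to be specific to upper GI bleeding.
- **The TIA gap shows only by comparison.** Table 9's ICD-9 entry is a wildcard, no text requires baseline and outcome lists to match, and TIA is secondary. All of this stands.
- **Blank cells are weak evidence.** The ICD-10 cell beside 434.x1 is also blank, apparently because I63.xxx spans two rows. This is fair, but the endarterectomy sentence itself names only an ICD-9 code.

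A reader might go further and infer a spurious drug difference, particularly for apixaban with its later window. The documents do not support that. Its dabigatran comparator is restricted to the same window (6,050 patients, against 16,604 in the rivaroxaban comparison), both arms face one code list at any date, and month and year of index date are considered for the propensity score. This protection is not complete: Section 9.7 leaves the final covariate list open, and matching on a score balances index date rather than time on treatment. Bias is therefore possible only if ICD-10-era person-time differs between matched arms.

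**Conclusion.** The point holds as a defect in the consistency of outcome definitions. The endarterectomy gap matters most, because it broadens a primary outcome in the ICD-10 period if the lists are programmed as written. The GI gap is partly covered by other codes, and the TIA gap is one code in a secondary outcome; both run in the opposite direction.

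With an October 2015 switch and a 2-10% share of short endarterectomy stays, ischemic stroke counts would rise by about 2-11% in the ICD-10 period and roughly 0.3-2.4% over the whole study across the two comparisons. Both inputs are assumptions, and the whole-study figure further assumes events spread evenly over time. No size can be given for the GI and TIA gaps from the documents. The effect is on absolute rates and on comparability across coding eras; a biased treatment comparison has not been shown.

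**What to change.** 1. Add the ICD-10 procedure codes for carotid endarterectomy to the ischemic stroke exclusion in Table 9.
2. Add the ICD-10 partner of 44.43 to the upper GI row, after confirming that 0W3P8ZZ from Table 7 suits that sub-outcome.
3. Align the TIA outcome list with Table 2 by adding G45.2, or state why it is left out.
4. Report outcome rates by coding era as a check, and compare ICD-10-era person-time between the matched arms.

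No design change is needed. The cost is a code-list edit. Section 6 dates the start of programming-rule development to 19 October 2016 and of data analysis to 5 December 2016, both before the protocol date of 15 December 2016, so a rerun may also be needed.
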